7.2.7. Child Depression Rating Scale – Revised (CDRS-R)

The Child Depression Rating Scale – Revised¹⁷ (CDRS-R) is a clinician-rated scale that assesses 17 distinct symptom areas to derive an index of depression severity. Though originally developed for children 6-12 yrs, it has been widely used with adolescents and its developers recommend it for both children and adolescents.¹⁸ Clinicians' ratings are based on information obtained from interviews with both child and parent (or guardian) informants;

interview guides have been developed to structure the interview to ensure all 17 symptom areas are assessed. For this trial, the manual's recommendations on resolving discrepancies between informants will be used (ie, most impaired rating given by valid informant will be assigned). It takes about 20-30 min to administer and rate the CDRS-R. Ratings are assigned on a 7-point scale (ranging from 1-7, with higher values indicating greater impairment). A total scale score is calculated by summing the 17 items. The total score on the CDRS-R will be used to assess changes in depression severity over time between treatment groups.

7.2.8. Movement Disorder Scales

The following scales will be used to assess symptoms and findings related to Parkinsonism, akathisia, and abnormal involuntary movements. Investigators will be instructed to record movement disorders as adverse events (AEs) only if they are clinically meaningful. Specifically, investigators will be asked to record the disorder as an adverse event only if (1) clinically meaningful movement disorder side effects are observed or are volunteered by the subject, (2) a clinically meaningful movement disorder is present at baseline and increases in severity, or (3) concomitant therapy (benztropine, benzhexol, or other anticholinergics or propranolol) is initiated or reinstated for movement disorders while the subject is participating in the study. All dystonic movements are to be recorded as AEs unless present at the same severity at baseline.

7.2.8.1. Simpson-Angus Rating Scale (SARS)

The Simpson-Angus Rating Scale¹⁹ (SARS) will be administered to assess parkinsonian symptoms and related extrapyramidal side effects through observation of the subject. The scale contains 10 items, including gait, arm dropping, shoulder shaking, elbow rigidity, wrist rigidity, leg pendulousness, glabellar tap, tremor, and salivation. The head rotation item (from the modified Simpson-Angus Rating Scale) will be substituted for the original #7 item, head dropping. Seven of the ten items measure parkinsonian rigidity. Each item is rated on an anchored 5-point scale, with 0 = the absence of the condition or normal and 4 = the most extreme form of the condition. A total score is obtained by adding all of the scores of the individual items. The SARS takes approximately 10 minutes to administer.

7.2.8.2. Barnes Akathisia Rating Scale (BAS)

The Barnes Akathisia Rating Scale²⁰ (BAS) will be administered to assess akathisia. The scale is designed to rate akathisia through observation of restless behavior and questioning of the subject to determine the degree of subjective restlessness and distress associated with restlessness. A global clinical rating completes the assessment.

The first 3 items of the BAS (Objective, Subjective, and Distress related to restlessness) are rated on a 4-point scale (0-3). The fourth item, the global clinical assessment of akathisia, uses a 6-point scale (0-5). Only the global clinical assessment measure from this scale will be analyzed. Higher scores indicate increased severity. All ratings are anchored. The BAS takes approximately 10 minutes to administer.

7.2.8.3. Abnormal Involuntary Movement Scale (AIMS)

The Abnormal Involuntary Movement Scale²¹ (AIMS) will be used to document occurrences of dyskinesias in subjects, specifically tardive dyskinesia. The scale incorporates observation and brief examination of the subject and consists of 12 items. Items 1-4 assess the severity of orofacial movements. Items 5-7 assess extremity and truncal dyskinesias. Items 8-10 rate global severity of movements as indicated by the examiner's judgment of the severity of abnormal movements (item 8), the examiner's judgment of the subject's incapacitation due to the movements (item 9), and the subject's awareness of the movements and associated distress (item 10). Items 11-12 concern the subject's dental status.

Items 1-10 are rated on a 5 point (0-4) anchored severity scale with 0 = none, 1 = minimal, may be normal, 2 = mild, 3 = moderate, and 4 = severe. Items 11 and 12 are questions with yes/no answers. Only the sum of the first 7 items will be analyzed. The AIMS can be completed in 5-10 minutes.

7.2.9. Suicidality Assessments

7.2.9.1. Suicidality Assessments at Screening

A risk assessment should be done if the subject's responses on any of the screening instruments or other screening information indicate that:

- The subject has had suicide ideation associated with actual intent and/or plan at any time in their lifetime such that a positive response ('Yes') is made on items 4 or 5 of the suicidal ideation subscale of the C-SSRS; or
- The subject has any lifetime history of suicide behaviors such that a determination of 'yes' is made to any of the suicide behavior items of the C-SSRS; or
- In the investigator's judgment a risk assessment is required.

A written copy of the risk assessment should be included in the subject's clinical record (source documentation).

7.2.9.2. Suicidality Assessments at Baseline and Post-baseline Visits

At the baseline visit (visit 2) and post-baseline visits, the C-SSRS will be administered. If there are 'yes' answers on items 4 or 5 of the suicidal ideation subscale of the C-SSRS or any behavioral questions of the C-SSRS, a risk assessment should be done to determine whether it is safe for the subject to continue to participate in the trial. If there are any 'yes' answers on items 4 or 5 of the suicidal ideation subscale of the C-SSRS or any behavioral questions of the C-SSRS at the post-baseline visits, supplemental information should be collected and the appropriate CRFs completed for the purpose of constructing a narrative that allows a detailed description of the adverse event(s) and outcome(s). Supplemental information will also be collected for a completed suicide.

A written copy of the risk assessment should be included in the subject's clinical record (source documentation).

7.2.9.3. Columbia-Suicide Severity Rating Scale (C-SSRS)

The Columbia-Suicide Severity Rating Scale (C-SSRS)²² will be used to evaluate suicide ideation and severity at screening, baseline, and each post-baseline visit. The C-SSRS is a semi-structured interview that captures the occurrence, severity, and frequency of suicide-related thoughts and behaviors during the assessment period. The interview includes definitions and suggested questions to solicit the type of information needed to determine if a suicide-related thought or behavior occurred. The C-SSRS is the prospective counterpart to the Columbia Classification Algorithm of Suicide Assessment (C-CASA) categorization system.²³ Responses to individual C-SSRS items can be mapped directly to the C-CASA categories (ie, completed suicide, attempted suicide, preparatory acts, suicidal ideation, non-suicidal self-injurious behavior) for summary and analysis purposes. The C-SSRS has been broadly used in numerous industry sponsored randomized clinical trials (RCTs) in both CNS and non-CNS indications.

The C-SSRS is available in a Baseline version and a “Since Last Visit” version. The baseline version assesses suicidal behavior over the lifetime and suicidal ideation at the time the subject was most suicidal. The “Since Last Visit” version assesses suicidal ideation and behavior between visits in a clinical trial. The clinician administering the interview should use information provided by the subject as well as other sources of information (eg, from parent(s) or guardian(s)) to determine if suicidal ideation or behavior occurred.

The C-SSRS contains 2 required items pertaining to suicidal ideation, 4 required items pertaining to suicidal behavior, and 1 required item pertaining to non-suicidal self-injurious behavior. There are 8 additional suicidal ideation items and 2 additional suicidal behavior items which are completed in cases of positive responses for other items, as well as 2 items for completed suicide and suicide behavior present during the interview. Thus, there is a maximum of 19 completed items.

The Suicidal Ideation items are rated on a dichotomous scale (yes or no). There is also an Intensity of Ideation subscale, which assesses the Frequency, Duration, Controllability, Deterrents, and Reasons for Ideation associated with the Most Severe suicide ideation reported by the patient, using 5-point Likert scales. The Suicidal Behavior items and the Non-Suicidal Self-Injurious Behavior items are also scored dichotomously yes or no. In addition, the total number of attempts (including interrupted and aborted attempts) is recorded. This is followed by a Lethality subscale which rates the Actual Lethality/Medical Damage and Potential Lethality of the attempt on 5- and 3-point Likert scales, respectively. A total score can be generated for the Intensity of Ideation portion of the interview. Otherwise, no other total scores are generated. In the event of a positive categorical response the interviewer can provide text or narrative that further describes the thought or behavior.

For subjects who are ages 7-11 at the Screening Visit, the Children’s Since Last Visit version of the C-SSRS should be utilized, even if the child has his/her 12th birthday during participation in this study. The Since Last Visit version refers to the subject’s experience since their last visit.

For subjects who are ages 12-17 at the Screening Visit, the Since Last Visit version of the C-SSRS should be utilized. The Since Last Visit version refers to the subject's experience since their last visit.

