4.2. Exclusion Criteria

Subjects presenting with any of the following will not be included in the study:

1. Subjects who are investigational site staff members directly involved in the conduct of the trial and their family members, site staff members otherwise supervised by the Investigator, or subjects who are Pfizer employees directly involved in the conduct of the trial.
2. Subjects who are clinically stable on treatment regimens that are being well tolerated.
3. Subjects with substance-induced psychotic disorder or whose behavioral disturbance is thought to be due to substance abuse.
4. Subjects with DSM-V defined Substance Use Disorder (including psychoactive substance or alcohol use disorders) within the preceding 1 month of screening (does not apply to nicotine or caffeine).
5. Subjects who are judged by the investigator as being at imminent risk of suicide.
6. Subjects who are judged by the investigator as being at imminent risk of homicide.
7. Subjects should be excluded or a risk assessment should be done to verify that it is safe for the subject to participate in the trial if the subject's responses on any of the screening instruments or other screening information based on the investigator's judgment indicate:
 - A suicide ideation associated with actual intent and a method or plan at any time in their lifetime such that a positive response ('Yes') is made on items 4 or 5 of the suicidal ideation subscale of the C-SSRS;
 - Any lifetime history of suicide behaviors such that a determination of 'yes' is made to any of the suicide behavior items of the C-SSRS. Subjects with significant Intellectual Disability (ie, Intelligence Quotient (IQ) <70) that would interfere with study conduct or with the interpretation of the study assessments.
8. Subjects with significant Intellectual Disability (ie, Intelligence Quotient (IQ) <70) that would interfere with study conduct or with the interpretation of the study assessments.

9. Subjects with Autism Spectrum Disorder (including autistic disorder, Rett syndrome, childhood disintegrative disorder, pervasive developmental disorder – not otherwise specified (PDD-NOS), Asperger syndrome).
10. Subjects with Disruptive Mood Dysregulation Disorder.
11. Subjects with schizophrenia, schizoaffective disorder, schizophreniform disorder, or delusional disorder.

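### Protocol 7.2.9.3 names only Since Last Visit forms of the C-SSRS and assigns the lifetime form to no visit, although the suicidality entry criterion relies on lifetime C-SSRS answers

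*Protocol*

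**What the plan says.** Protocol 7.2.9.3 schedules the C-SSRS at screening, at baseline and at each later visit, and describes two forms. "The C-SSRS is available in a Baseline version", and of that form it says: "The baseline version assesses suicidal behavior over the lifetime and suicidal ideation at the time the subject was most suicidal". The second form, Since Last Visit, has a shorter reach: this "version assesses suicidal ideation and behavior between visits in a clinical trial".

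The section closes with the instructions on which form to use, by age. For the older band: "For subjects who are ages 12-17 at the Screening Visit, the Since Last Visit version of the C-SSRS should be utilized". For ages 7-11 a children's form of the same type is named: "Since Last Visit version of the C-SSRS should be utilized, even if the child has his/her 12th birthday during participation in this study". Both are followed by the same reminder of the recall period: "The Since Last Visit version refers to the subject’s experience since their last visit".

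Three other places in the protocol look back over the subject's whole life:

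- Exclusion 7 in Section 4.2 calls for exclusion or a risk assessment on lifetime ideation shown by a yes on C-SSRS ideation items 4 or 5, or on behavior. The behavior limb begins "Any lifetime history of suicide behaviors such that a determination of" and goes on to a yes on any C-SSRS behavior item.
- Section 7.2.9.1 has the same two limbs for the screening risk assessment. The second begins "The subject has any lifetime history of suicide behaviors such that a determination of" and again ends in a yes on the C-SSRS.
- Footnote k, attached to the C-SSRS row of the Schedule of Activities, asks for a risk assessment on lifetime ideation with intent or plan, or on any earlier suicidal behavior.

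**The concern.** The entry rule asks a lifetime question and looks for the answer in C-SSRS items. The only form the protocol tells sites to use asks about the time since the last visit. A first screening visit has no earlier study visit, so at that point the interval form has no defined recall period, and on the protocol's own description it does not reach back over a lifetime.

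What is at stake is a safety screen in children and adolescents with acute mania who may be randomized to placebo. A child with a past attempt and nothing recent could answer no throughout an interval form, so the C-SSRS limb of exclusion 7 would not flag the case. There is also a smaller question for the analysis: the planned tables of worsening and new-onset suicidality depend on what the reference assessment looked back over, and the documents do not say.

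**Working it through.** No arithmetic applies. The check is whether any statement about the C-SSRS links a form to a visit, and whether the recall period of that form matches what the entry rule needs.

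**Step 1. Which form is assigned, and where.**

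| Place | Form named | Visit named for that form |
|---|---|---|
| Protocol 7.2.9.3, instruction for ages 12-17 | Since Last Visit | none |
| Protocol 7.2.9.3, instruction for ages 7-11 | Children's Since Last Visit | none |
| Protocol 7.2.9.3, description of the scale | Baseline and Since Last Visit both described | none |
| Protocol 6.1 and 6.2 (screening, baseline) | none; both refer to 7.2.9 | not applicable |
| Protocol 6.3 to 6.5 (later visits) | none; all refer to 7.2.9 | not applicable |
| Protocol 7.2.9.2 (baseline and post-baseline) | none | not applicable |
| Schedule of Activities, C-SSRS row and footnote k | none | not applicable |
| Protocol 9.9, SAP 6.2.2 and SAP 8.2.6 | none | not applicable |

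The Baseline version is described once and assigned nowhere. The visit lists send the reader to 7.2.9, where the only instructions on form are the two age-band sentences. The trial enrolls ages 10-17, so 10-11 falls in the first band and 12-17 in the second. No subject is left outside them.

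**Step 2. What each form covers.** By 7.2.9.3, the Baseline version covers lifetime behavior and ideation at its worst point; the Since Last Visit version covers the interval between visits.

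**Step 3. What the entry rule needs.** Exclusion 7 and 7.2.9.1 need lifetime answers on ideation items 4 and 5 and on the behavior items, and both name the C-SSRS as the place where a yes is recorded. Footnote k needs the same lifetime reach.

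**Step 4. Put together.** The form assigned (interval) and the look-back required (lifetime) do not match at screening. The form that would match is available but unassigned.

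**Step 5. The analysis reference.** Protocol 9.9 and SAP 8.2.6 plan tables of post-baseline worsening and new onset without defining the reference. The general rule in SAP Section 6 takes the pre-dose assessment at the Baseline Visit when a variable is measured there, and the C-SSRS is measured at Visit 2. On that rule the reference is Visit 2. The look-back of the Visit 2 form is not stated, so the meaning of new onset is left open.

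**The case against.** The strongest reply is that the age-band sentences are being misread. In them, the mention of the Screening Visit fixes the subject's age for choosing the children's or the standard form; the clause about a 12th birthday during the study shows this. It does not say that the interval form is the one used at screening. Since 7.2.9.3 describes a lifetime form, and 4.2 and 7.2.9.1 presuppose lifetime answers at screening, the authors probably meant the Baseline version to be given there. This stands: a reader might infer that the protocol orders the interval form at screening, and the text does not go that far. What remains is a missing assignment. The reader who supplies it must still guess whether the Baseline version belongs to Visit 1 (screening) or to Visit 2, which the protocol calls the baseline visit. Rater training cannot be counted on to settle it, because Section 7.4 exempts raters with current C-SSRS certification from retaking the training.

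The second reply is that past suicidality has other ways to surface. Exclusion 7 accepts any screening instrument and other screening information. Section 7.2.9.1 adds investigator judgment as a trigger of its own. Section 6.1 requires a psychiatric history, a clinical interview and the K-SADS. Exclusion 5 separately covers imminent risk. This also stands. A reader might infer that exclusion or risk assessment would certainly fail to be triggered; the documents do not support that. They support only that the C-SSRS, the one scheduled instrument dedicated to suicidality, could miss the history.

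**Conclusion.** The inconsistency is real and worth correcting. Followed literally, 7.2.9.3 gives a screening C-SSRS that would not return the lifetime answers on which exclusion 7 and 7.2.9.1 rely. This rests on the protocol's own account of what each form covers and on the absence of any other assignment in either document. It bears on the form, not on the whole screening process.

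Its reach is every screened subject, because both age bands carry the same wording. The number of subjects whose history would be missed cannot be estimated. A reader might be tempted to size it from the five cases of suicidal ideation and one overdose reported for Study A1281123 in Protocol 1.2.2.1.1. Those were events during that study, in a population that also included schizophrenia and schizoaffective disorder, and pre-existing ideation is only one of the explanations given. They say nothing about lifetime history missed at screening.

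A reader might also infer that the new-onset tables lose a lifetime reference. That is not established: neither document defines new onset against lifetime history, and the SAP's general rule points to Visit 2. The supportable statement is that the reference and its look-back are unspecified. Sample size, power, type I error and the primary analysis are unaffected.

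**What to change.** 1. In Protocol 7.2.9.3 and in the C-SSRS row of the Schedule of Activities, state which version, in its age-appropriate form, is used at each visit. The version given at screening should have the lifetime look-back that the entry criterion already requires, and the Since Last Visit wording should be limited to the later visits it fits. This reconciles 7.2.9.3 with exclusion 7, Section 7.2.9.1 and footnote k.
2. Leave the wording of exclusion 7 and its sources of information unchanged.
3. In SAP 8.2.6, state which C-SSRS assessment, with which look-back, is the reference for the worsening and new-onset tables. For subjects already screened, describe the form that was in fact given. A lifetime form completed after randomization is not a remedy, because it could record on-study events as history.

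The cost is a short paragraph and a Schedule entry in a protocol amendment, one sentence in the SAP, and a check that sites hold the right form for each visit. No eligibility threshold and no analysis model changes.

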7.2.10. Subject Contact

Contact should be made with the subject by the investigator or designated staff member, either by telephone or in person as an unscheduled visit, after the baseline visit but before Visit 3 and after Visit 3 but before Visit 4 to ensure that the subject is taking the proper capsules at the proper time and to monitor the tolerability, safety, and efficacy of the titration plan/study drug.

7.3. Efficacy Assessments

7.3.1. Young Mania Rating Scale (YMRS)

The YMRS is an 11-item instrument used to assess the severity of mania in patients with a diagnosis of bipolar disorder. The 11 items are: Elevated Mood, Increased Motor Activity Energy, Sexual Interest, Sleep, Irritability, Speech (Rate and Amount), Language - Thought Disorder, Content, Disruptive - Aggressive Behaviour, Appearance, and Insight. It has operationally-defined anchors, and is based on patient self-report combined with clinician observations. The YMRS will be administered using the Kowatch interview guide, which adapts the scale for pediatric populations. It requires 15-30 minutes to complete. The YMRS was developed for the assessment of mania severity in hospitalized adults, but its validity in pre-pubertal patients has been demonstrated, and it is now widely accepted and used as a primary measure of mania severity in outpatient studies of children and adolescents with bipolar disorder.^{24,25}

The YMRS must be administered by an appropriately qualified and experienced individual who has completed the Pfizer rater training program. For each subject, the same rater should administer the YMRS at each of the indicated timepoints. A co-rater who has successfully completed the Pfizer rater training program may administer the YMRS in lieu of the primary rater, on rare occasions when the primary rater is unavailable due to illness or other unavoidable circumstances.

7.3.2. Clinical Global Impression Scales (CGI-S and CGI-I)

The Clinical Global Impression (CGI) Scale²⁶ is a standardized assessment tool used to rate the severity of a subject's illness and improvement over time. The CGI using two subscales: Severity of Illness (CGI-S) and Global Improvement (CGI-I). The CGI-S assesses the rater's impression of the subject's current illness state. Scores range from 1 (not ill at all) to 7 (among the most extremely ill). The CGI-I subscale rates the subject's improvement or worsening from baseline. Scores range from 1 (very much improved) to 7 (very much worse).

CCI

CCI

7.4. Rater Qualifications/Training/Certification for Diagnostic, Efficacy, and Safety Rating Scales

For this study, a central contract research organization (CRO) will work with the Sponsor to verify that raters meet the rating scale qualification criteria for the study and are trained on administration of the scales. This will apply to raters identified at the start of the study as well as those raters that may need to be added during the life of the study.

Potential raters who fully meet the education and clinical experience described below will be allowed to continue with rater training without Sponsor review. Potential raters who do not fully meet these criteria will require individual review by the central CRO and the Sponsor for potential inclusion in rater training. A final determination will be made by the Sponsor as to whether the potential rater can or cannot proceed to training. Once evaluated and documented an individual rater may receive the approval to rate on a specific scale based on their education level and prior clinical experience. When a rater has been approved based upon their education and experience as described above, they will be granted access to the study specific training materials. Once all scale specific training is satisfactorily completed, documentation of training completion by the central CRO will occur. Upon receipt of the documentation by the central CRO, a rater can begin administration of the specific scale(s) for the study.

Criteria for Training Approval without Sponsor Review

Rating Scale	Educational Level*	Prior Clinical and Pediatric Experience	Prior Scale Experience
C-SSRS	MD or DO; PhD in Clinical or Counseling Psychology; RN or Master's level degree in a medical, social work, or mental health field.	≥1 year clinical experience with pediatric population and/or pediatric clinical trial experience.	Prior training with C-SSRS within the past two years with valid documented certification will exempt rater from having to retake C-SSRS training. **

Rating Scale	Educational Level*	Prior Clinical and Pediatric Experience	Prior Scale Experience
YMRS	Child and Adolescent Psychiatrist (or in the case of countries outside the US, the local country equivalent in education and training); or Adult Psychiatrist (PI or Sub Investigator (SubI) or Doctoral Level Psychologist.	≥1 year clinical experience with pediatric population and/or pediatric clinical trial experience.	5 administrations of any clinician rated interview based scale such as CCI CDRS-R, Montgomery and Asberg Depression Rating Scale (MADRS), Hamilton Depression Scale (HAM-D).
	MD, MA, MS, MSW, RN, BS, BA	≥1 year clinical experience with pediatric population and/or pediatric clinical trial experience.	5 administrations of any clinician rated interview based scale.
CGI	Child and Adolescent Psychiatrist (or in the case of countries outside the US, the local country equivalent in education and training) or Adult Psychiatrist; (PI or SubI) or Doctoral Level Psychologist.	≥1 year clinical experience with pediatric population and/or pediatric clinical trial experience.	5 administrations of the CGI or similar type global rating scale such as Clinical Global Impression of Change Scale (CGIC).
CCI	CCI	CCI	CCI

Rating Scale	Educational Level*	Prior Clinical and Pediatric Experience	Prior Scale Experience
	CCI ███████████		
	CCI ███████████	C C I ███████████	CCI ███████████
K-SADS	Child and Adolescent Psychiatrist (or in the case of countries outside the US, the local country equivalent in education and training); or Adult Psychiatrist (PI or SubI) or Doctoral Level Psychologist.	≥1 year clinical experience with pediatric population and/or pediatric clinical trial experience.	5 administrations of any diagnostic interview based scale such as Structured Clinical Interview for DSM-IV (SCID), Mini-international neuropsychiatric interview (MINI), Mini International Neuropsychiatric Interview for Children and Adolescents (MINI-KID), Diagnostic Interview Schedule (DIS), Composite International Diagnostic Interview (CIDI).
AIMS/BARS/SAS	Child and Adolescent Psychiatrist (or in the case of countries outside the US, the local country equivalent in education and training); or Adult Psychiatrist or other physician.	≥1 year clinical experience with pediatric population and/or pediatric clinical trial experience.	5 administrations of any movement scale such as AIMS/BARS/SAS or Extrapyramidal Symptom Rating Scale-A (ESRS-A), Unified Parkinson's disease rating scale (UPDRS) or the Global Dystonia Scale.

* International equivalencies will be accepted. Doctoral level psychologist (PhD or PsyD) must be trained in child development.

** Upon 2 year expiration of documented certification, raters will be required either to retake C-SSRS training or resubmit valid, current documented certification. Should the two years lapse during the course of the study, retraining updated training and a renewed certificate will be required.

CCI

